2.3.2.2 Efficacy Endpoints

The secondary efficacy endpoints are to assess the effect of treatment with Orenitram after an induction period with Remodulin on the following parameters:

- Change in 6-Minute Walk Distance (6MWD) from Baseline to the Transition Visit and Week 16
- Change in Borg dyspnea score from Baseline to the Transition Visit and Week 16
- Change in World Health Organization (WHO) Functional Classification (FC) from Baseline to the Transition Visit and Week 16
- Change in N-terminal pro-brain natriuretic peptide (NT-proBNP) levels from Baseline to the Transition Visit and Week 16

5. Change in Echocardiographic parameters from Baseline to the Transition Visit and Week 16

Echocardiogram (ECHO) examinations as assessed by central reader will be conducted at the time points listed in Table 1. Several echocardiographic parameters will be collected, including: right atrial area (cm²), tricuspid annular plane systolic excursion (mm), RV free wall strain (%), RV/left ventricular ratio at diastole, RV diastole (mm), LV diastole (mm), Eccentricity Index systole, Eccentricity Index diastole, RV Myocardial Performance Index; Pulmonary Artery Acceleration Time (msec) and presence of PV Notching (Non-evaluable, Present or Not Present); LVOT dimension (mm), LVOT vti (cm), ECHO Heartrate (bpm), cardiac output (Doppler method) (L/min) and presence of pericardial effusion (Present/ Not Present)

- 6. Change in PAH symptom score from Baseline to the Transition Visit and Week 16
- 7. The percentage of subjects that improve in each of the following 4 individual clinical parameters at Week 16 (6MWD, NT-proBNP, WHO FC, right atrial area) to a lower risk stratum, as defined by the 2015 European Society of Cardiology guidelines, compared to Baseline
- The percentage of subjects that meet each of the following 4 individual clinical parameters at Week 16 in the low risk category, as defined by the 2015 European Society of Cardiology guidelines: 6MWD >440 meters, serum NT-proBNP <300 ng/L, WHO FC I or II, and right atrial area <18 cm²

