- 9. The percentage of subjects that either achieve an Orenitram dose of 4 mg TID (or a total daily dose of 12 mg) or higher at Week 16 (or a dose of 0.057 mg/kg TID [or a total daily dose of 0.171 mg/kg] or greater for subjects <70 kg) or the percentage of subjects that achieve an Orenitram dose ≥2 mg TID and <4 mg TID (or a total daily dose ≥6 mg and <12 mg) at Week 16, with at least 2 of the following 3 clinical parameters at Week 16 calculated and summarized: 6MWD increase by ≥10% or ≥30 meters from Baseline, serum NT-proBNP reduction >30% from Baseline, or WHO FC I or II. This will performed using both prescribed total daily dose as well as actual dose taken.
- 10. The percentage of subjects that successfully transitioned to Orenitram at any dose and were successfully maintained on therapy at Week 16
- 11. Change in Subjects' Treatment Satisfaction Questionnaire for Medication (TSQM) responses and Health-related quality of life (emPHasis-10) questionnaires from Baseline to the Transition Visit and Week 16

The prescribed total daily dose will be used for secondary efficacy endpoints when applicable, unless otherwise stated.

TSQM

The questionnaire is provided in protocol Appendix G. The TSQM (version 1.4) comprises 14 items across four domains focusing on effectiveness (three items Q1-Q3), side effects (five items Q4-Q8), convenience (three items Q9-Q11), and global satisfaction (three items Q12-Q14) of the medication over the previous 2–3 weeks, or since the patient's last use. Except for item 4 (presence of side effects; yes or no), all items have five or seven responses, scored from one (least satisfied) to five or seven (most satisfied). Item scores are summed to give four

domain scores, which are in turn transformed to a scale of 0-100. Item 4 is not included for scoring. If an item score is missing and half of the items in the domain are complete, domain scores may be imputed from the person-specific mean score of completed items (i.e., the domain scores will be calculated as the total score of the completed items divided by the possible maximum total score of the completed items and times 100). For example, if a subject has Q1 = 5, Q2 = 2 and Q3 is missing, then domain score effectiveness = (5+2)/(7+7)*100 = 50. The calculated domain scores will be listed.

emPHasis-10

The questionnaire is provided in protocol Appendix H. The emPHasis-10 comprises 10 items. Each item has a score scale of 0-5. The total score will be calculated as

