3.4.1 Primary Efficacy Endpoint

The number and percentage of subjects achieving an Orenitram dose of 4 mg 3 times daily (TID) (or a total daily dose of 12 mg) or higher (or a dose of 0.057 mg/kg TID [or a total daily dose of 0.171 mg/kg] or greater for subjects <70 kg) will be summarized for Week 16 for the Per-Protocol population. Subjects with missing data for prescribed total daily dose at Week 16 will be considered as not achieving the primary efficacy endpoint.

This will be repeated for the Completer Population.

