3.4.2 Secondary Efficacy Endpoints

Secondary efficacy endpoints will be summarized by visit, as applicable. The change from Baseline at each visit will be summarized for each parameter. For study visits occurring after the Transition Visit, the change from Transition Visit will also be summarized for each parameter in addition to the change from Baseline. The continuous secondary endpoints will also be summarized on Transition Visit and X Weeks Post Transition Visit in addition to the nominal visits. The value of interest listed in section 2.3.2.2 will be provided.

- 6-Minute Walk Distance (6MWD)
 - The subjects receiving oxygen during the time of the test will be listed
 - The subjects having unusual circumstances that adversely affected the walk will be listed
- Heart rate recovery after 6MWD
- Borg dyspnea score
 - The Borg dyspnea scores and their respective shifts from baseline and Transition Visit will be summarized for each assessment (i.e. number and percent of subjects who improved, worsened, or had no change)
- World Health Organization (WHO) Functional Classification (FC)
 - The functional class values and their respective shifts from baseline and Transition Visit will be summarized for each assessment (i.e. number and percent of subjects who improved, worsened, or had no change)
- N-terminal pro-brain natriuretic peptide (NT-proBNP)
 - o The percent change from Baseline and Transition Visit will also be provided.
- · Echocardiographic parameters
- PAH symptom score
 - Severity grade values (i.e., 0, 1, 2, or 3) for each symptom of PAH (fatigue, dyspnea, edema, dizziness, syncope, chest pain, and orthopnea) will be listed for all subjects. The severity grades and their shifts from baseline and Transition Visit will be summarized for each assessment.
- Subjects' TSQM responses and Health-related quality of life (emPHasis-10) questionnaires

- The number and percentage of subjects that successfully transitioned to Orenitram at any dose and were successfully maintained on therapy at Week 16
- The number and percentage of subjects that improve in each of the following 4 individual clinical parameters (6MWD, NT-proBNP, WHO FC, right atrial area) to a lower risk stratum, as defined by the 2015 European Society of Cardiology guidelines, compared to Baseline will be provided for the Transition Visit and Week 16.

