- The number and percentage of subjects that meet each of the following 4 individual clinical parameters in the low risk category, as defined by the 2015 European Society of Cardiology guidelines: 6MWD >440 meters, serum NT-proBNP <300 ng/L, WHO FC I or II, and right atrial area <18 cm². This will be provided for the Transition Visit and Week 16.
- The number and percentage of subjects that either achieve an Orenitram dose of 4 mg TID (or a total daily dose of 12 mg) or higher (or a dose of 0.057 mg/kg TID [or a total daily dose of 0.171 mg/kg] or greater for subjects <70 kg) or the percentage of subjects that achieve an Orenitram dose ≥2 mg TID and <4 mg TID (or a total daily dose ≥6 mg and <12 mg), with at least 2 of the following 3 clinical parameters: 6MWD increase by ≥10% or ≥30 meters from Baseline, serum NT-proBNP reduction >30% from Baseline, or WHO FC I or II. This will be provided for the Transition Visit and Week 16. This will be performed using both prescribed total daily dose as well as actual dose taken.

The continuous secondary endpoints may be analyzed using linear regression models with the endpoint [such as change in 6-Minute Walk Distance, change in log(NT-proBNP), and change in log(echocardiographic parameters) (performed by study sponsor at a later time) from Baseline to Transition Visit and Week 16] as the dependent variable and the baseline [or log(baseline)] value as a covariate. For endpoints modeled on the original scale, the predicted mean change from Baseline at the median baseline value will be provided, along with its associated standard error and 95% confidence interval. For endpoints modeled on the log scale, the predicted mean change from Baseline at the median log(baseline) value, with associated standard error and 95% confidence interval, will be back-transformed to the original scale and presented as the predicted geometric mean ratio to Baseline at the median baseline value. For each model fitted, the slope and its standard error and p-value will also be provided.

For patients in the Per-Protocol Population with a missing secondary efficacy endpoint at Week 16 for 6MWD, WHO FC, NT-proBNP or Echocardiographic parameters, the last observation carried forward (LOCF) method will be used, in addition to a separate complete case analysis. No imputation is needed for the Completer population.

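### Week 16 risk percentages (SAP items 7 and 8) carry forward or drop subjects who died or withdrew, while the Per-Protocol primary analysis counts them as not achieving; item 9 has no missing-dose rule

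*SAP*

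**What the plan says.** - **Primary endpoint (SAP 3.4.1).** In the Per-Protocol Population, "Subjects with missing data for prescribed total daily dose at Week 16 will be considered as not achieving the primary efficacy endpoint". The section then adds: "This will be repeated for the Completer Population".
- **Secondary endpoints (SAP 3.4.2).** For Per-Protocol subjects with a "missing secondary efficacy endpoint at Week 16 for 6MWD, WHO FC, NT-proBNP or Echocardiographic parameters", the plan is that "the last observation carried forward (LOCF) method will be used, in addition to a separate complete case analysis". Orenitram dose is not among the parameters named.
- **Item 7** counts subjects who improve on each of four parameters: "6MWD, NT-proBNP, WHO FC, right atrial area) to a lower risk stratum".
- **Item 8** is described in SAP 2.3.2.2 as "The percentage of subjects that meet each of the following 4 individual clinical parameters at Week 16 in the low risk category", with the cut-offs "6MWD >440 meters, serum NT-proBNP <300 ng/L, WHO FC I or II, and right atrial area <18 cm²". Right atrial area is one of the echo parameters listed under item 5.
- **Item 9** is met by reaching the primary dose threshold, or by a lower-dose limb in which subjects "achieve an Orenitram dose ≥2 mg TID and <4 mg TID (or a total daily dose ≥6 mg and <12 mg) at Week 16" and also satisfy at least two of three clinical criteria.
- **Populations.** Per-Protocol (SAP 3.2.2) requires study drug and no major deviation, but not completion. Completer (SAP 3.2.3) requires completion and being on Orenitram at Week 16. Secondary endpoints are summarised in both, and in the completers who met the primary endpoint.
- **Early withdrawal.** SAP 3.4 reports Week 16 and early study withdrawal separately in the efficacy tables.

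**The concern.** Items 7 and 8 state what share of subjects are in a favourable state at Week 16. A subject who has died, or has left because of worsening, is not in that state. Protocol 4.3.1 also requires withdrawal when another approved PAH treatment is added, so some withdrawals will themselves reflect inadequate response.

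Neither planned rule treats such a subject as not meeting the criterion by reason of having left. LOCF asks only what the last value was, and complete case removes the subject. The Completer summaries exclude these subjects by definition. The Per-Protocol primary analysis counts the same subject as not achieving, so two percentages in one report could treat one person in opposite ways.

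The study is descriptive and no formal test is planned, so no error rate is at stake. What is at stake is how the reported Week 16 percentages are read.

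**Working it through.** The plan gives no dropout rate or expected response for these items, and it states that no formal sample size computation was done. There is no planned figure to reproduce.

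**Which value would be carried**

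- WHO FC and 6MWD are scheduled at every post-Baseline visit, so the carried value may be recent.
- After Baseline, NT-proBNP and echo are scheduled only at the Transition Visit and at Week 16/Early Study Withdrawal (SAP Table 1). Without a withdrawal visit, the carried value is the Transition value or the Baseline value. For NT-proBNP, the Transition sample precedes Orenitram.
- The SAP does not say whether a Baseline value may be carried. For item 7 that would mean no improvement, hence not met. For item 8 it could mean met: Protocol 4.1 admits WHO FC II, which already satisfies the FC criterion.

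**Item 9**

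The lower-dose limb needs a Week 16 dose in range as well as the clinical criteria. Dose is not on the LOCF list, and early-withdrawal data are kept apart from Week 16. Carried clinical values therefore cannot by themselves make a subject without a Week 16 dose a success. They matter only where the Week 16 dose is known and a clinical value is missing. However, the rule that a missing dose counts as not achieving is written only for the primary endpoint, so a complete case analysis could drop the subject from item 9.

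**Formulas for items 7 and 8**

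Let N be the Per-Protocol subjects, d those with no Week 16 value, r the responders among the N − d observed, and c the leavers whose last value meets the criterion (0 ≤ c ≤ d).

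- Failure rule: r/N
- Complete case: r/(N − d), higher than r/N whenever r > 0 and d > 0
- LOCF: (r + c)/N, equal to r/N if c = 0 and higher otherwise

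**Illustration**

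SAP 2.2.3 plans about 35 evaluable subjects and defines evaluable as completing the Week 16 visit without a relevant major deviation. Leavers are therefore additional to the 35, and N = 35 + d. Assumed: r = 18, all completers measured, and no major deviation among leavers.

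| Leavers d | N | Failure rule 18/N | Complete case 18/35 | LOCF, c = 0 to d |
|---|---|---|---|---|
| 1 | 36 | 50.0% | 51.4% | 50.0% to 52.8% (19/36) |
| 3 | 38 | 47.4% | 51.4% | 47.4% to 55.3% (21/38) |
| 5 | 40 | 45.0% | 51.4% | 45.0% to 57.5% (23/40) |

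With 5 leavers, complete case exceeds the failure rule by 6.4 points and LOCF exceeds it by 0 to 12.5 points.

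The range was widened to 14 or 21 responders among the 35 and 2 to 7 leavers:

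- The complete-case excess runs from 2.2 points (14/35 − 14/37 = 40.0% − 37.8%) to 10.0 points (21/35 − 21/42 = 60.0% − 50.0%).
- The LOCF excess runs from 0 to 16.7 points (7/42).

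**The case against.** Several stronger readings are tempting, and the documents do not support them.

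- *A reader might infer that LOCF turns leavers into item 9 successes.* It does not, because the Week 16 dose is not carried.
- *A reader might infer that both rules always inflate the percentages.* Under LOCF, a subject whose last value fails the criterion counts as not meeting it, exactly as under the failure rule. The LOCF excess is zero or upward, and its upper bound requires every leaver to have last met the criterion.
- *A reader might infer that the primary endpoint always counts leavers as failures.* That holds for the Per-Protocol analysis only. The Completer repeat leaves them out.
- *A reader might infer that the SAP expressly applies LOCF to the percentages.* Its sentence names parameters, not the derived items. Applying it to items 7 and 8 is the natural reading. If that was not intended, those items have no rule and need the same clarification.

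The protocol also limits the problem. Section 3.6 asks subjects who stop study drug to stay to Week 16 and be assessed. Section 7.3.7 asks for all assessments before withdrawal. A worsening subject may thus have a late value that shows it. Two missing-data analyses are already planned, and with counts, population sizes and disposition reported, a reader could work out r/N for items 7 and 8.

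These points narrow the concern and reduce its likely size. They do not help where no withdrawal visit takes place, death being the clearest case, and they do not give items 7 to 9 a rule consistent with the primary analysis.

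**Conclusion.** The point stands in a limited form. For Per-Protocol subjects who died or withdrew, items 7 and 8 would, on the natural reading, rest on an earlier value or omit the subject, contrary to the rule the SAP uses for its own Per-Protocol primary analysis. For item 9, the fault is a missing-dose rule that was never extended beyond the primary endpoint.

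The size depends on numbers the documents do not give. With the assumed 18 responders, 35 evaluable completers and 5 leavers, the same data yield 45.0%, 51.4%, or anything from 45.0% to 57.5%, according to the rule and the leavers' last values. With few leavers the gap is small. It is an inexpensive improvement worth making, with no inferential consequence.

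**What to change.** Add to SAP 3.4.2, for items 7, 8 and 9 in the Per-Protocol Population:

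1. A subject with no Week 16 value or dose because of death or study withdrawal counts as not meeting the criterion. The denominator is all Per-Protocol subjects, as for the primary endpoint.
2. LOCF and complete case are kept as labelled sensitivity analyses for these percentages, and as planned for the continuous summaries. State whether a Baseline value may be carried.
3. State the rule for a subject who attends Week 16 but lacks a single parameter, such as an unreadable right atrial area. This case should not be left without a rule.
4. Footnote each table with the number classed as not meeting the criterion by rule.

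The denominator should be the Per-Protocol Population by name, since the SAP defines only the Safety, Per-Protocol and Completer sets. The change needs SAP wording and minor programming, and no new data. The cost is that the reported percentages become less favourable when subjects have left.

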3.1.4 Definition of Treatment Phases

"Remodulin phase" is defined as the portion of the study when a patient is receiving Remodulin only.

"Transition phase" is defined as the portion of the study beginning at the Transition Visit when a patient is receiving both Remodulin and Orenitram. "Transition phase" ends at the last dose of Remodulin if the transition is "successful". "Transition phase" ends at the last dose of Orenitram if the transition is "unsuccessful" and reversed. "Transition phase" ends at the last dose of Orenitram and Remodulin if the transition is stopped.

"Orenitram phase" is defined as the portion of the study when a patient is receiving Orenitram only.

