3.2.3 Completer Population

The Completer Population is defined as all subjects in the study who complete the study without any major deviations (which may interfere with efficacy evaluation) and are receiving Orenitram at Week 16.

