The secondary efficacy endpoints will be summarized for the Per-Protocol Population, the Completer Population, and the subgroup of patients in the Completer Population who met the primary endpoint.

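### SAP 3.4.2 reports Orenitram persistence and the Week 16 prescribed-dose composite in sets whose entry conditions largely or wholly fix the result, and gives no secondary efficacy display on all treated subjects

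*SAP*

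**What the plan says.** **Where the endpoints are reported.** SAP 3.4.2 sends all secondary efficacy endpoints to the Per-Protocol set and also to "the Completer Population, and the subgroup of patients in the Completer Population who met the primary endpoint". No secondary endpoint is exempted.

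**Who is a Completer.** Under SAP 3.2.3 a subject must complete the study, have no major deviation, and also "are receiving Orenitram at Week 16".

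**Item 10, persistence.** SAP 3.4.2 asks for the number and percentage who "successfully transitioned to Orenitram at any dose and were successfully maintained on therapy at Week 16". The SAP does not define success for this endpoint. The nearest text is SAP 3.1.4, where the transition phase "ends at the last dose of Remodulin if the transition is" successful.

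**Item 9, composite.** SAP 2.3.2.2 begins: "The percentage of subjects that either achieve an Orenitram dose of 4 mg TID (or a total daily dose of 12 mg) or higher", with the same weight-based threshold for subjects under 70 kg as the primary endpoint. The alternative route is 2 to below 4 mg TID with at least two of three clinical parameters. It is to be computed on both prescribed and actual dose.

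**Dose basis.** SAP 3.4 makes prescribed total daily dose (TDD) the default for primary and secondary endpoints.

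**Protocol.** Protocol 10.3 places all safety and efficacy analyses on the Safety Population, meaning everyone who received study drug. SAP 3.2.1 keeps that set for safety only. SAP Section 5, on changes from the protocol, lists an interim analysis and a new sample size but not this change.

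**The concern.** A percentage is informative only if members of the set could have failed the endpoint. In the Completer set, almost nobody can fail persistence. In the primary-responder subgroup, nobody can fail the composite on prescribed dose. These cells would still sit in the efficacy tables in the same format as real results, and a figure of 100% is easily lifted into an abstract without its denominator.

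Persistence matters most here. The protocol's rationale (1.1 and 1.3) is that adverse events lead to early Orenitram discontinuation, and its hypothesis (1.4) is that induction improves tolerability. The natural denominator is everyone who started treatment, and SAP 3.4.2 has no such display.

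A related matter is the responder-only summary of 6MWD, NT-proBNP and functional class. That subgroup is selected on a Week 16 outcome. Under protocol 6.1, titration proceeds as tolerated, and transition may be withheld, stopped or reversed because of PAH symptoms or safety concerns. Tolerability and clinical course therefore help decide who enters the subgroup.

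**Working it through.** The documents give no expected rates and no formal sample-size calculation, so there is no plan figure to reproduce. The check is set logic.

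**Step 1. Item 10 in Completers.**
- Completer = study completed, no major deviation, on Orenitram at Week 16 (SAP 3.2.3).
- Item 10 = successfully transitioned at any dose and successfully maintained at Week 16 (SAP 3.4.2).
- Being on Orenitram at Week 16 is in substance the endpoint, so the result is about 100% in the Completer set and in its responder subgroup.
- Exceptions are possible. One is a subject still cross-tapering. A transition on schedule starts by Day 57 + 5 = 62 and, at 21 days, ends on Day 82, well before Day 113 − 7 = 106. This exception therefore needs a late start, which protocol 6.1 allows for subjects first judged unsuitable. Others are subjects whose transition was reversed and repeated, or whose dosing was interrupted. Whether they count as successful is undefined.

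**Step 2. Item 9 in primary responders, Week 16, prescribed dose.**
- Primary met: TDD ≥ 12 mg, or ≥ 0.171 mg/kg if under 70 kg (SAP 3.4.1).
- Composite met: primary thresholds met, **or** TDD ≥ 6 and < 12 mg with at least 2 of 3 clinical parameters.
- Primary met therefore implies composite met. Enumerating TDD from 0 to 74.6 mg in 0.375 mg steps, weight from 40 to 120 kg, and 0 to 3 parameters met gives 55,228 combinations that meet the primary endpoint. None fails the composite.
- Missing doses do not break this. SAP 3.4.1 counts a missing prescribed dose as not achieving the primary endpoint, so such a subject never enters the subgroup.

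**Step 3. Item 9 on actual dose.** A missed dose counts as 0 mg (SAP 3.4.1.1). Two end-of-transition doses from protocol Appendix I, with one of three doses missed:
- 70 kg, 5 mg TID: prescribed 15 mg; actual 15 × 2/3 = 10 mg. This is below 12 mg, so response now depends on the clinical parameters.
- 40 kg, 2.875 mg TID: prescribed 8.625 mg against a threshold of 0.171 × 40 = 6.84 mg, so the primary is met. Actual 8.625 × 2/3 = 5.75 mg, below both 6.84 and 6 mg, so the composite fails whatever the parameters.

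The actual-dose version can therefore fall below 100% in responders.

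**Step 4. Size of the gap, as an illustration.** All rates here are assumptions. Take 35 treated subjects as a convenient denominator; the SAP's figure of about 35 refers to evaluable subjects, so the number treated would be larger. Let 24 to 32 be on Orenitram at Week 16, all of them Completers. Let 60–80% of these meet the primary endpoint, and 0–50% of the rest qualify by the second limb.

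| Endpoint | All treated | Completers | Primary responders |
|---|---|---|---|
| Item 10 | 24/35 to 32/35 (69–91%) | about 100% | about 100% |
| Item 9, prescribed, Week 16 | 14/35 to 29/35 (40–83%) | 14/24 to 29/32 (58–91%) | 100% |

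Only the fixed cells follow from the SAP; the other entries move with the assumptions.

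**The case against.** The strongest reply is that little is at stake. The Per-Protocol set is not conditioned on Week 16 Orenitram use, so both endpoints receive an informative percentage in the same summary. SAP 3.3.1 also tabulates, on all enrolled subjects, those who began and completed transition, returned to Remodulin, or discontinued study drug before the Week 16 assessments. The sets are openly named, no formal testing is planned (SAP 3.1.6), and the SAP draws no dose-effect claim from the responder subgroup. All of this stands, and it is why the point is minor.

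A reader might infer more than the documents support:

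- **That true persistence would be hidden.** It would not, given the Per-Protocol and disposition tables. What is missing is the endpoint itself on all treated subjects, with major deviators included.
- **That the composite is 100% in responders whatever the data.** This holds only at Week 16 on prescribed dose. It also takes the two-of-three clinical condition to qualify only the 2 to below 4 mg TID limb. That is the natural reading, but the sentence could be clearer.
- **That the responder subgroup is defined by the composite.** It is defined by the primary endpoint, which is one limb of it.
- **That responder-only clinical results have nothing to be compared with.** The full Completer column is shown too. Non-responder counts follow as n(C) − n(R), and means as [n(C)·mean(C) − n(R)·mean(R)] / [n(C) − n(R)]. SDs follow in the same way from sums of squares. Only medians, quartiles and extremes cannot be recovered.

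A side-by-side responder and non-responder display is a matter of preference. On a small post-baseline split it could itself invite a dose-effect reading.

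**Conclusion.** The concern holds, at minor severity. Persistence is about 100% in both Completer displays by the entry condition, subject to the undefined meaning of success. The Week 16 composite on prescribed dose is exactly 100% in primary responders under the natural either/or reading. These values say nothing about treatment.

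No estimate elsewhere is biased and no planned information is lost. The substantive gap is that SAP 3.4.2 has no secondary efficacy display on the Safety Population, although protocol 10.3 assigns efficacy to that set. How far the 100% figures would differ from an all-treated figure cannot be known from the documents; the 69–91% range for persistence rests entirely on assumed rates.

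**What to change.** In SAP 3.4.2:

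1. Report item 10 on the Safety Population (all treated) and the Per-Protocol set only. Mark it not applicable in both Completer displays.
2. Mark item 9 on prescribed dose at Week 16 not applicable in the primary-responder subgroup. Keep the actual-dose version.
3. Define successful transition and successful maintenance for item 10, and state that the clinical condition in item 9 applies only to the lower-dose limb, if that is what is meant.
4. Label the responder-only clinical summaries as a post-baseline selection that does not estimate a dose effect. A column for Completers who did not meet the primary endpoint is optional.

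The cost is SAP wording and a few table shells, with no new data and no change to trial conduct. The downside for the sponsor is that a few favourable-looking cells disappear.
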